#### **9.5 Outliers**

Descriptive statistics will be used to identify outliers in any key variables. Suspected outliers will be included in all analyses unless there is sufficient scientific justification to exclude them.

---

## 9.6 Distributional Characteristics

Time to event endpoints will be evaluated with the non-parametric log-rank test. The semi-parametric proportional hazards model will be used to estimate the treatment hazard ratio with and without stratification which assumes the hazard for events are proportional over time between the treatment arms within strata.

Log-log curves will be plotted to assess the hazard proportionality between treatment arms. The curves will be repeated by randomization stratum. If the hazards are proportional between treatment arms, the curves must be parallel. Also, KM curves should not cross (unless the hazards are similar which means no treatment difference).

The assumption of proportional hazards will be investigated adding a treatment\*log(time) interaction in the Cox model. If the hazards are proportional between treatment arms, the treatment\*log(time) interaction must be non-significant (see code fragment in [Appendix B](#)).

A Kolmogorov-type supremum test will be used to test the proportional hazards assumption for treatment comparison based on an analysis of cumulative residuals overall and within the randomization strata (Lin, Wei, and Ying, 1993, see code fragment in [Appendix B](#)).

The diagnostic approaches described before will be conducted by the study statistician and no official output will be provided unless necessary.

If the proportional hazards assumption is strongly violated, then an alternative analysis will be considered. A stratified piece-wise Cox model will be used to allow estimation of an overall weighted-average hazard ratio as well as within interval treatment hazard ratios (Collett 2003). Three intervals will be used in the piecewise model, one from time 0 to 12 months, one from time 12 to 24 months, and the other beyond 24 months (see code fragment in [Appendix B](#)), other intervals may be evaluated to assess sensitivity.

## 9.7 Validation of Statistical Analyses

Programs will be developed and maintained and output will be verified in accordance with current risk-based quality control procedures.

Tables, figures and listings will be produced with validated standard macro programs where standard macros can produce the specified outputs.

The production environment for statistical analyses consists of Amgen-supported versions of statistical analysis software, for example the SAS System version 9.4 or later.

## 10. Statistical Methods of Analysis

### 10.1 General Principles

All analyses will be descriptive with no formal hypothesis testing.

In principle, mean, standard deviation, median, first and third quartiles, minimum and maximum will be calculated for continuous variables; frequency and percent will be calculated for binary and categorical variables. Graphical summaries of the data may also be presented.

Analyses of tumor tissue or serum biomarkers may be performed after collection of all samples during the conduct of the study and therefore may be reported after the primary analysis of efficacy endpoint.

The primary analysis for efficacy endpoints will be performed on the Intent to Treat Analysis Set by randomized treatment. In addition, some of the analysis may be repeated on the Efficacy Analysis Set by treatment actually received. Safety analyses will be conducted on the Safety Analysis Set.

Data analysis is scheduled to occur at the following time points:

- Two interim analyses with no formal stopping rules will be performed when approximately 40 and 75 subjects randomized to talimogene laherparepvec have had the opportunity to complete the safety follow-up visit. (Please refer to [section 8.1](#) for details).
- An additional third interim analysis with no formal stopping rule is planned to evaluate RFS approximately 1 year after the end of randomization. This analysis will be conducted by the Amgen study team. (Please refer to [section 8.1](#) for details).
- The primary analyses for RFS will occur at the later time of either the occurrence of approximately 64 events (local, regional, or distant recurrence of melanoma or death) or approximately 2 years after end of randomization. The primary analysis for certain secondary endpoints (eg, response to neoadjuvant treatment, R0 resection rate, pCR rate, and safety) will be performed using the data from the second interim analysis.
- The final analyses will occur approximately 5 years after the end of randomization. An additional analysis will also occur approximately 3 years after the end of randomization.
- Ad hoc analyses for safety or some efficacy endpoints (eg, response to neoadjuvant treatment, R0 resection rate, pCR rate) may be conducted before the planned primary and/or final analyses if interim data are required for submission to regulatory authorities. These ad hoc analyses will be executed by the **Amgen study** team.

## 10.2 Subject Accountability

The number of subjects in each of the strata at randomization will be summarized by randomized treatment.

A subject disposition summary table will be produced. The number of subjects screened, randomized who are treated (talimogene laherparepvec or/and surgery) and not treated will be tabulated by randomized treatment. Reasons for discontinuation of talimogene laherparepvec and not receiving surgery, end of study status (completed vs. did not complete), reason for not completing the study, the status of completing safety follow-up, and the reason for not completing safety follow-up will also be summarized by randomized treatment. The number of screen failure subjects and screen failure reasons will also be provided.

## 10.3 Important Protocol Deviations

Important Protocol Deviations (IPDs) categories are defined by the study team before the first subject's visit and updated during the IPD reviews throughout the study prior to database lock. These definitions of IPD categories, deviation codes and descriptions will be used during the course of the study. The final IPD list is used to produce the summary of IPDs table and the list of subjects with IPDs by deviation category, subcategory, and randomized treatment. A separate summary table and listing will also be provided for inclusion/exclusion deviations.

Subjects with the IPDs considered affecting efficacy outcomes will be excluded from the Efficacy Analysis Set (see [Section 7.3](#)).

## 10.4 Demographic and Baseline Characteristics

Summary statistics of the **following demographic and baseline disease characteristics** will be tabulated by randomized treatment arm on the Intent To Treat Analysis Set:

- **Region: USA or non-USA**
- **Age at baseline: < 50, ≥ 50; < 65, ≥ 65; < 75, ≥ 75 years**
- **Sex: male or female**
- **Number of measurable tumors at baseline**
- **Presence of uninjected tumors at baseline and during the treatment: yes vs no (Arm 1 only)**
- **The sum of the products of the two largest perpendicular diameters of baseline measurable lesions (SPD)**

- **Histogenetic subtype: acral lentiginous melanoma vs desmoplastic vs lentigo maligna melanoma vs nodular melanoma vs superficial spreading melanoma vs unclassifiable vs missing**
- **Current disease stage (IVRS): IIIB nodal vs IIIB in transit vs IIC nodal vs IIIC in-transit with nodal vs IV M1a**
- **Current disease stage (CRF): IIIB vs IIIC vs IV M1a**
- **Time from initial histological diagnosis of melanoma to study entry**
- **Baseline absolute lymphocyte count:  $\leq 1000$  vs  $> 1000$**
- **Recurrent disease  $\geq 1$  year from primary diagnosis vs recurrent disease  $< 1$  year from primary diagnosis vs no prior melanoma**
- **Baseline ECOG performance status: 0 vs 1**
- **BRAF mutation status: mutation present vs mutation not present vs missing**
- **Baseline HSV-1 status: negative vs positive vs equivocal vs unknown**
- **Previous systemic anti-cancer therapy for melanoma: yes vs no**
- **Previous systemic immune check-point inhibitor therapy for melanoma: yes vs no**
- **Prior surgical procedures: yes vs no**
- **Prior radiotherapy: yes vs no**
- **Planned adjuvant therapy (IVRS): adjuvant systemic therapy with or without radiotherapy vs radiotherapy without adjuvant systemic therapy vs none**

## **10.5 Efficacy Analyses**

The following table ([Table 2](#)) summarizes the efficacy endpoints and planned analysis methods.

**Table 2. Study Design Characteristics Example Endpoint Summary Table**

Endpoint	Primary Summary and Analysis Method	Sensitivity Analysis
Primary Endpoint		

 
• RFS
 
	
 
• Log-rank test and 80% CI for the treatment hazard ratio from a proportional hazards model without stratification in the ITT analysis set.
 
• Kaplan-Meier (K-M) estimation by randomized treatment arm.
 
• Simultaneous 80% confidence band for each arm KM estimate from 1 to 5 years per equal-precision band method.
 
• 80% CI for K-M quartiles by arm (where estimable) per Brookmeyer & Crowley.
 
• 80% CI for between-arm quartile difference in KM estimate via bootstrap.
 
	
 
• Repeat with stratification by the two randomization factors
 
• If 10% or more of the overall recurrence (both arms combined) occur within the first 6 months post-surgery, the stratified analysis will be repeated with stratified piece-wise Cox model to estimate within interval hazard ratios adjusting for randomization factors.
 
• Estimate the Cox model hazard ratio with Robins IPCW weighting censoring RFS at the start of all or selected adjuvant therapy for melanoma.
 
• If warranted (eg, the planned adjuvant therapy stratification factor is discordant with the actual for > 10% of all subjects), the stratified analysis will be repeated replacing planned adjuvant therapy with actual adjuvant therapy and/or adjuvant therapy containing selected types of systemic therapy, including immunotherapy.
 
• Cox model and KM analysis of RFS according to randomized treatment and actual adjuvant systemic therapy (yes vs no) with 3 comparisons: all subjects, those with adjuvant systemic therapy, and those without adjuvant systemic therapy.
 
• Repeat with and/or without stratification by the two randomization factors in the efficacy analysis set, if necessary.
 
• Univariate and multivariate proportional hazards models without stratification may be used to explore the prognostic and/or predictive value of baseline covariates using primary endpoint definition and alternative endpoint definition #1 in Section 4.1.1.
 
• Subgroup analyses will be evaluated with a log-rank test and corresponding proportional hazard model without stratification using primary endpoint definition and alternative endpoint definition #1 in Section 4.1.1.
 
• Repeat subgroup analyses with a log-rank test and proportional hazards model with stratification by two randomization factors.
 
• Repeat using sensitivity analysis alternative endpoint definitions (see Section 4.1.1).
 
• Repeat based on the type of anti-cancer therapy received: any subsequent anti-cancer therapy, adjuvant anti-cancer therapy for melanoma, non-adjuvant anti-cancer therapy for melanoma using primary endpoint definition and alternative definition # 1 in Section 4.1.1. Subjects who receive the respective subsequent anti-cancer therapy type prior to an RFS event will be censored at the last evaluable tumor assessment prior to receiving the respective subsequent anti-cancer therapy type.
 


**Table 2. Study Design Characteristics Example Endpoint Summary Table**

Endpoint	Primary Summary and Analysis Method	Sensitivity Analysis

Key Secondary Endpoints
 
 
• OS
 
• DMFS
 
• LRFS
 
• RRFS
 
	
 
• The same methods described for the primary endpoint.
 
	
 
• Excluding OS, repeat with stratification by two randomization factors.
 
• For LRFS, assess the equality between treatment groups using Gray's test, and estimate treatment HR with 95% CI stratified by the randomization factors using subdistribution proportional hazards model, with distant recurrence as competing risk.
 
• DMFS will be compared with Gray's test and the subdistribution proportional hazards model with censoring considered a competing risk if the subject has a primary reason for ending the study after a local or regional recurrence of withdrawal of consent or lost to follow-up.
 
• RRFS will be compared with Gray's test and the subdistribution proportional hazards model with censoring considered a competing risk if the subject has a primary reason for ending the study after a local recurrence of withdrawal of consent or lost to follow-up.
 

 
• Landmark RFS, LRFS, RRFS, DMFS by year;
 
• Landmark OS by year
 
	
 
• 80% CI for the K-M estimate in the ITT analysis set by randomized treatment arm with s.e. per Greenwood.
 
• 80% CI for the between-arm difference with s.e., per Greenwood.
 
	
 
• Excluding OS, repeat using the alternative endpoint definition #1 in Section 4.1.1.
 

**Table 2. Study Design Characteristics Example Endpoint Summary Table**

Endpoint	Primary Summary and Analysis Method	Sensitivity Analysis
Key Secondary Endpoints		

 
• Rate of R0 surgical resection;
 
• Rate of pCR
 
	
 
• 80% exact CI by randomized treatment arm in the ITT analysis set per Clopper-Pearson.
 
• 80% approximate exact CI for the between-arm difference per Wilson's score method with continuity correction.
 
	
 
• Repeat using the efficacy analysis set, if necessary.
 
• Multivariate logistic models may be used to explore the prognostic and/or predictive value of baseline factors.
 

Tumor response (Arm 1 Only): 
 
• Overall Tumor Response (per Investigator)
 
• Individual injected lesion response overall and by subtype (cutaneous / subcutaneous vs lymph node)
 
• Individual uninjected lesion response overall and by subtype (cutaneous / subcutaneous vs lymph node)
 
• Subject response on overall injected lesions
 
• Subject response on overall uninjected lesions
 
	
 
• For response rate use the Clopper-Pearson method to calculate exact 80% CIs;
 
• For time to response the Kaplan-Meier (K-M) estimate
 
• The tumor response analysis is performed in the ITT analysis set.
 
	
 
• Repeat using the efficacy analysis set, if necessary.
 

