 - Arm 1: day 1 of week 12 (\pm 2 weeks) or within 1 week prior to surgery if a subject ends talimogene laherparepvec prior to week 12
- Response assessment per modified WHO response criteria ([Appendix D](#))
 - Arm 1: day 1 of week 12 (\pm 2 weeks) or within 2 weeks prior to surgery if a subject ends talimogene laherparepvec prior to week 12
- Histological tumor assessment of the surgical specimens. Surgical specimens will be assessed for presence of viable tumor and tumor margin status for cutaneous and subcutaneous tumor.
 - Tumor-free margins (negative margins, R0) resection is defined by pathologist as absence of ink on the tumor. All other resections of viable tumor are described as tumor positive margins resections, and are defined as
 - R1 resection - complete resection with no grossly visible tumor left behind as defined by the surgeon, or
 - R2 resection - partial resection with grossly visible tumor left behind as defined by the surgeon.
 - A pathological complete response (pCR) in Arm 1 is defined as no evidence of viable tumor cells on complete pathological evaluation of the surgical specimen per institutional standards of care
- Recording of adverse events at each visit
- Recording of serious adverse events at each visit. Serious adverse events will be reported to Amgen within 24 hours following the investigator's knowledge of the event

- Documentation of concomitant medications at each visit
- Arm 1 - Reporting pregnancy in a female subject or a female partner of a male subject while the subject is taking talimogene laherparepvec treatment and through 3 months after end of treatment ([Section 9.3](#))
- Arm 1 - Reporting lactation case in a female subject while the subject is taking talimogene laherparepvec treatment and through 3 months after end of treatment ([Section 9.3](#))
- Talimogene laherparepvec administration
 - Arm 1: day 1 of weeks 1, 4, 6, 8, 10, and 12 or until all injectable tumors have disappeared, intolerance of study treatment, whichever occurs first. Subjects who experience growth in existing tumors or the appearance of new tumors will be allowed to remain on talimogene laherparepvec treatment until week 12 of therapy unless, in the opinion of the investigator and in consultation with the sponsor's medical monitor, immediate surgical resection or any other treatment for melanoma is warranted.
- Surgery

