10.1.2 Analysis Sets

Intent to Treat Analysis Set

The primary analysis of all efficacy endpoints of the study will be conducted on the intent to treat analysis set defined as all randomized subjects who were randomized to either treatment arm. All subjects will be analyzed according to their treatment randomization.

Safety Analysis Set

The safety analysis set will include all subjects who received talimogene laherparepvec or surgical resection of melanoma tumor lesion(s). The safety analyses will be performed by treatment received.

Efficacy Analysis Set

The efficacy analysis set will include all subjects in Arm 1 who received at least one dose of talimogene laherparepvec and surgical resection of melanoma tumor lesion(s) and all the subjects in Arm 2 who received surgical resection of melanoma tumor lesion(s). In addition, all subjects in the efficacy analysis set must have achieved histopathologic tumor-free margin (R0) status after surgery and should not have any important protocol deviations which may affect the efficacy endpoints. The efficacy analysis set may be used for sensitivity analysis of efficacy endpoints if needed.

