Prior systemic anti-cancer therapies for melanoma include chemotherapy, chemoradiotherapy, immunotherapy, targeted biologics, targeted small molecules, and chemo-embolization which are not in the setting for adjuvant or neoadjuvant treatment.

- Previous Systemic Immune Check-Point Inhibitor Therapy for Melanoma

Previous systemic immune check-point inhibitor anti-cancer therapies (eg, anti-CTLA4, anti-PD1) not in the setting for adjuvant or neoadjuvant treatment.

- Subsequent Anti-Cancer Therapy for Melanoma after Recurrence

Subsequent anti-cancer therapy for melanoma is defined as any anti-cancer therapy (or treatment) received for melanoma after recurrence. Subsequent anti-cancer therapy for melanoma will be collected from CRF form “Subsequent Anti-Cancer Therapies for Current Malignancy”.

- Adjuvant therapy for Melanoma

Adjuvant therapy is defined as anti-cancer therapy subjects receive after surgical resection of melanoma lesion(s) but before recurrence. Adjuvant therapy will be collected from CRF form “Subsequent Anti-Cancer Therapies for Current Malignancy”.

- Landmark OS by year

Estimated proportion of subjects alive at each year by the Kaplan-Meier method.

- Landmark RFS by year

Estimated proportion of subjects experiencing overall recurrence (local, regional, distant) at each year by the Kaplan-Meier method.

- Response (Arm 1 only)

Refer to [Section 4.1.2.1.1](#).

- Best overall response (BOR) per investigator (Arm 1 only)

Best response for a subject is the best overall response observed across all time points in the following order: CR, PR, SD, PD or UE.

- Histopathology Tumor-free margin (R0) Surgical Resection Rate

Histopathology tumor-free margin (R0) surgical resection is defined by pathologist as absence of ink on the tumor for all disease. R0 surgical resection rate is defined as proportion of subjects with R0 resection. For each subject, the R0 resection status (R0 or non-R0) will be derived from lesion level resection status collected from CRF. In order for a subject to count as an R0 resection event, all lesion observations will be R0 within the given subject. Any observation of a non-R0 (R1, R2) for a subject will make the subject a non-R0 case for this endpoint.

- Pathological Complete Response (pCR) Rate (Arm 1 Only)

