Pathological Complete Response (pCR) is defined as no evidence of viable tumor cells on complete pathological evaluation of the surgical specimen per institutional standards of care. pCR rate is defined as proportion of subjects which achieves a pCR. For each subject, the pCR status (pCR or non-pCR) will be determined based on whether or not viable tumor was detected in the surgical specimen.

- Last Valid Tumor Evaluation

For overall tumor response per modified WHO response criteria the last valid tumor evaluation refers to the last valid tumor response assessment (PR, CR, SD or PD) per investigator. For the subject-level tumor response based on the tumor burden of a subset of lesions (injected, uninjected lesions, or other subtype) or the lesion-level response the last valid tumor evaluation refers to the assessment where the corresponding tumor burden or the corresponding individual tumor area is not missing.

- Baseline Lesion

Lesions measured at the most recent visit on or before receiving the first administration of talimogene laherparepvec (i.e., study day 1) will be flagged as baseline lesions. Baseline lesions must have positive tumor area. Lesions reported in the baseline measurable lesion CRF page but with a tumor area of zero or missing value at the last measurement on or before study day 1 will not be considered baseline lesions.

- New Lesion

New lesions are those that first appear after study day 1 with a positive tumor area or lesions without a positive lesion area in the last assessment on or before study day 1

but a positive lesion area from follow up tumor measurements. Baseline tumor area of a new lesion is obtained from the earliest date with positive bi-dimensional tumor measurements after study day 1. If a new lesion(s) that appears in between scheduled tumor response assessments disappear(s) before the next scheduled assessment, there is no need to include this lesion for tumor response evaluation

- Evaluable Lesion

A baseline or new measurable lesion is defined as evaluable if it has an initial positive area followed by at least 1 assessment with a non-missing area.

- Injected/Uninjected Lesion

Baseline or new lesions that are reported as injected with talimogene laherparepvec at any time during the treatment period are considered injected lesions. Baseline or new lesions that are not reported as injected with talimogene laherparepvec are considered uninjected lesions.

- Baseline Tumor Burden

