## 7.3 Efficacy Analysis Set

The efficacy analysis set will include all subjects in Arm 1 who received at least one dose of talimogene laherparepvec and surgical resection of melanoma tumor lesion(s) and all the subjects in Arm 2 who received surgical resection of melanoma tumor lesion(s). In addition, all subjects in the efficacy analysis set must have achieved histopathologic tumor-free margin (R0) status after surgery and should not have any important protocol deviations considered to affect efficacy outcomes listed in [Section 10.3](#).

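### The optional repeat of the R0 rate in the Efficacy Analysis Set gives 100% in both arms by construction, and the same set is expected to raise the Arm 1 pCR rate

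*SAP*

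**What the plan says.** SAP Table 2 (Section 10.5) makes ITT the primary population for the R0 rate, the pCR rate and tumor response. In the sensitivity column, both the R0/pCR row and the tumor-response row carry the entry "Repeat using the efficacy analysis set, if necessary". The only other entry for R0 and pCR is an optional multivariate logistic model.

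SAP 7.3 requires surgery in both arms and at least one dose of talimogene laherparepvec in Arm 1. It then adds that "all subjects in the efficacy analysis set must have achieved histopathologic tumor-free margin (R0) status after surgery", and it removes subjects with deviations judged to affect efficacy. Protocol 10.1.2 sets the same R0 condition and says: "The efficacy analysis set may be used for sensitivity analysis of efficacy endpoints if needed".

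The endpoint definitions are in SAP Section 6:

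- **R0 rate:** "R0 surgical resection rate is defined as proportion of subjects with R0 resection". At subject level, "Any observation of a non-R0 (R1, R2) for a subject will make the subject a non-R0 case for this endpoint".
- **pCR rate (Arm 1 only):** "pCR rate is defined as proportion of subjects which achieves a pCR", where pCR means "no evidence of viable tumor cells on complete pathological evaluation of the surgical specimen per institutional standards of care".

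On margins, protocol 7.2.2 first defines R0 and then says: "All other resections of viable tumor are described as tumor positive margins resections".

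**The concern.** A sensitivity analysis should be able to give a different answer from the primary one. For R0, the condition for entering the set is the endpoint itself, so the repeat has only one possible result. For pCR, the same condition trims the denominator in a way that depends on the pathology result. Tumor response is assessed no later than resection (SAP 4.1.2.1.1), so restricting it to R0 subjects selects on something that happens afterwards.

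These endpoints carry weight. Protocol 2.3 expects part of the benefit to come through more R0 resections. R0, pCR and response have their primary analysis at the second interim (protocol 10.4.3, SAP 10.1). SAP 8.1 also names them for possible ad hoc analyses for regulatory submission. The Efficacy Analysis Set repeat is the only alternative-population check listed for them, and the SAP states no trigger for deciding that it is necessary.

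**Working it through.** The documents state no R0 rate, pCR rate or precision target for these endpoints, so there is no plan figure to reproduce. The R0 result needs only the definitions. The pCR sizes need assumed counts.

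**Inputs.** About 150 subjects randomized 1:1, so about 75 per arm (SAP 3.2). 80% intervals: Clopper-Pearson within arm, and the Wilson score method with continuity correction between arms (SAP Table 2, Appendix B.4). Assumed, not in the documents: 30, 45, 60 or 68 R0 subjects of 75, and 11 pCR subjects in Arm 1.

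**R0 rate.** Let E be the number of subjects in the set in one arm. All E are R0, so the rate is E/E = 1 in each arm and the difference is 1 − 1 = 0. An example with assumed counts:

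| | Arm 1 | Arm 2 | Difference (80% CI) |
|---|---|---|---|
| ITT | 60/75 = 80.0% | 45/75 = 60.0% | +20.0 points (9.5 to 29.9) |
| Efficacy Analysis Set | 60/60 = 100% | 45/45 = 100% | 0 points (−4.1 to +5.4) |

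Assumed ITT differences of −20, 0, +10.7 and +20 points all become 0. The interval in the set reflects only how many subjects are in it. For example, the Clopper-Pearson lower limit is 92.6% for 30/30 and 96.2% for 60/60. A logistic model for R0 within the set could not be fitted, because the outcome does not vary.

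**pCR rate, Arm 1.** pCR means no viable tumor, and protocol 7.2.2 applies positive margins to resections of viable tumor. A pCR subject is therefore neither R1 nor R2. An unoperated subject has no specimen and cannot be pCR. If every pCR subject is coded R0 and all R0 subjects enter the set, then with P pCR subjects and R R0 subjects:

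- ITT rate = P/75
- Rate in the set = P/R
- Ratio = 75/R = 1/(Arm 1 R0 rate)

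With P = 11, the ITT rate is 11/75 = 14.7% (80% CI 9.6 to 21.3).

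| R0 subjects of 75 | Rate in the set | Ratio |
|---|---|---|
| 30 | 11/30 = 36.7% | 2.50 |
| 45 | 11/45 = 24.4% | 1.67 |
| 60 | 11/60 = 18.3% | 1.25 |
| 68 | 11/68 = 16.2% | 1.10 |

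**How far exclusions could undo this.** Hold the set at R subjects and keep a fraction k of the pCR subjects. The rate in the set falls below the ITT rate when kP/R < P/75, that is, k < R/75. More than 40% of pCR subjects would have to be lost at R = 45 (45/75 = 0.60), more than 20% at R = 60 (60/75 = 0.80), and more than about 9% at R = 68 (68/75 = 0.907). The direction is therefore secure at low R0 rates and less so at high ones.

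**Tumor response.** The documents do not link response to R0 status, so neither direction nor size can be computed. What can be said is that the set is chosen on an outcome later than the endpoint.

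**The case against.** The strongest reply is that little depends on this entry. It is conditional, ITT is primary for all three endpoints, no hypothesis is tested, and the detailed methods in SAP 10.5.2 do not mention this repeat for binary endpoints. A result of 100% against 100% would be recognised at once. All of that stands. It limits the consequence but does not give the R0 repeat any content.

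A reader might infer that Table 2 contradicts SAP 7.3, which names only the primary endpoint for this set. The documents do not support that. SAP 7.3 says the set will be used for that endpoint, not that it is reserved for it. SAP 10.1 and protocol 10.1.2 and 10.5.1 all allow wider use. The two SAP places should be aligned, but neither breaks a stated rule.

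A reader might also take the pCR inflation as a fixed factor. It is not. R0 is derived from lesion-level margin status on the CRF, while pCR comes separately from viable tumor in the specimen. The margin definition does not say outright that a pCR specimen is coded R0. Protocol 7.2.2 also ties margin status to cutaneous and subcutaneous tumor, so the coding of a subject with nodal disease only is unstated. Deviation and wrong-arm exclusions could remove pCR subjects too. Eligibility requires completely resectable disease, so a high R0 rate, with a factor near 1.1, is as admissible as a low one.

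Finally, nothing shows that the repeat would be presented as a per-protocol result. The R0 condition is stated openly, and a pCR rate among operated R0 subjects can be interpreted if labelled as such. It does not, however, test the robustness of the ITT rate.

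**Conclusion.** The point holds for R0 without any assumption: the listed repeat returns 100% in each arm and a difference of 0 for any data, and no section exempts this row from the R0 condition.

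For pCR the expected direction is upward, by about one over the Arm 1 R0 rate. The range of about 1.1 to 2.5 rests on assumed R0 counts of 68 down to 30 of 75, on pCR subjects being coded R0, and on deviation exclusions not falling mainly on pCR subjects. For tumor response, only selection on a later surgical outcome is established.

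It would go too far to say that the plan commits to reporting these repeats or that any primary estimate is affected. The entry is optional and the ITT results do not change.

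**What to change.** In SAP Table 2, delete the Efficacy Analysis Set repeat for the R0 rate.

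For any sensitivity repeat of R0, pCR or tumor response, define a separate set by two things only: absence of the eligibility deviations listed in SAP 7.3, and having started the assigned treatment (in Arm 1, at least one dose of talimogene laherparepvec). It should carry neither the R0 nor the surgery condition. Removing R0 alone is not enough, because SAP 7.3 would still require surgery and so drop unoperated Arm 1 subjects, who should stay in the pCR denominator as non-pCR. In Arm 2 surgery is the only assigned treatment, so the text should make clear that starting treatment is not a surgery condition there, and that unoperated subjects in either arm count as non-R0.

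Align SAP 7.3 with Table 2 so that both name the same endpoints and sets.

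The cost is SAP wording and one population flag, with no new data. The repeated pCR rate would be less favourable than in the current set.
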